## **11.0 Provisions to Monitor the Data and Ensure the Safety of Subjects**

*11.1 Describe the plan to periodically evaluate the data collected regarding both harms and benefits to determine whether subjects remain safe.*

Response: [name] is responsible for review of data on a regular basis to ensure that collected data is being entered correctly. All unforeseen events during the study tasks will be reported immediately to the principal investigator; if necessary, they will be reported to the IRB.

*11.2 Describe what data are reviewed, including safety data, untoward events, and efficacy data.*

Response: Data related to study tasks will be reviewed.

*11.3 Describe how the safety information will be collected (e.g., with case report forms, at study visits, by telephone calls with participants).*

Response: Safety information will be documented on the data collection tool as necessary.

*11.4 Describe the frequency of data collection, including when safety data collection starts.*

Response: [name] is responsible for collection and review of all data.

*11.5 Describe who will review the data.*

Response: [name]

*11.6 Describe the frequency or periodicity of review of cumulative data.*

Response: see above

*11.7 Describe the statistical tests for analyzing the safety data to determine whether harm is occurring.*

Response: Number of severe hypoglycemic events will be documented. The rate of severe hypoglycemia will be compared to historical data.

*11.8 Describe any conditions that trigger an immediate suspension of the research.*

Response: Episode of pancreatitis.

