#### **Visit 3**

- Insulin pump settings
- Total daily insulin dose
- Food diaries
- Download of continuous glucose monitor – mean weekly blood sugars
- Blood sugar records with reports of hypoglycemia
- Adverse effects
- Mean blood glucose excursion, glucagon release, and serum inflammatory markers during mixed meal tolerance test

*Describe any primary or secondary safety endpoints.*

**Response:** Adverse effects including nausea/vomiting, anorexia. Injection site reactions/pain. Rates of hypoglycemia. Clinical or biochemical evidence of pancreatitis.

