#### **Visit 1 Screening Day (day 0):**

- Review the subject's medical history and family medical history
- Review subject's blood sugars and insulin pump settings
- Measure height, weight, blood pressure and heart rate.
- The principal investigator will perform a physical exam.
- If hemoglobin A1c level is not recorded in the medical record within 2 weeks of visit 1, this test will be performed.
- Record mean total daily insulin dose (previous 72 hours) from insulin pump.
- Subjects will be advised to wear his/her continuous glucose monitor (CGM) for the next two weeks, changing sites as indicated by the manufacturer.
- For subjects who do not have a CGM, we will insert the Abbott Freestyle Libre Professional Device. This device will monitor glucose levels throughout the entire study period. Subjects will be advised to check blood sugars at least 4 times per day and at any occasion when symptoms of hypoglycemia develop.
- Subjects will be asked to keep a record of any episodes of hypoglycemia.
- Subjects will be asked to keep a 4 day food record (three days, 1 weekend day).
- Subjects will be advised to follow their usual diabetes care plan with respect to carbohydrate counting, diet and exercise.

**Visit 2 (Day 7):** Subjects will come fasting for this visit. They will bring the food records and diary of hypoglycemia to this visit. This visit will take approximately 4 hours. At this visit, the following procedures will be performed:

- Records of blood sugars and CGM data will be obtained from subjects wearing personal CGMs
- Subjects wearing the Freestyle LibrePro system will continue wearing the device unless it became dislodged during the study. A new device will be placed in this case.
- Blood sugars and insulin pump settings will be reviewed.
- Record mean total daily insulin dose (previous 72 hours) from insulin pump.
- A Mixed Meal Tolerance test will be performed (see below)

- Insulin pump settings will be adjusted to decrease the risk of hypoglycemia during liraglutide treatment. Basal rates will be decreased by 25% and meal boluses will be decreased by 33%.
- The first dose of liraglutide will be given at the study site. Subjects will be given 0.6 mg subcutaneously. Subjects will be taught how to use the delivery device at this visit.
- Subjects will be advised to take 0.6 mg of liraglutide subcutaneously every morning at about the same time.

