## **10.0 Data Management**

*10.1 Describe the data analysis plan, including any statistical procedures.*

*Response:* For statistical purposes, the **primary endpoint** of the study is to detect a difference between untreated and treated periods in the change from baseline in mean weekly blood glucose concentrations. The statistical analysis will be carried out using analysis of variance (ANOVA) and tested at the 0.05 level. The results will be computed as mean±SD.

The secondary end points based on glycemic changes will include the difference from baseline in standard deviations of the mean weekly glucose concentrations, mean fasting blood glucose concentrations, the duration of time spent in hyperglycemia ( $>150\text{mg/dL}$ ,  $>200\text{mg/dL}$ ,  $>250\text{mg/dL}$ ) and hypoglycemia ( $<70\text{mg/dL}$ ,  $<40\text{mg/dL}$ ), and insulin dosage. A reduction in the area under curve following the meal will constitute another secondary end point. Within subject comparisons of the magnitude of change from baseline will also be made for these glycemia related secondary endpoints using student's t-test. Comparisons for these and the primary endpoints will also be made using the paired t-test or Wilcoxon's test for paired data for each subject. Additional secondary end-points of the study will be change from baseline in 1) mean weekly blood glucose 2) glucagon area under the curve concentrations following meal challenge 3) change in daily insulin dose (total dose and units/kg) 4) caloric intake based on 4 day food records and 5) change in serum adiponectin and CRP levels before and after initiation of liraglutide treatment. The relation between change in postprandial sugars, glucagon, and total daily insulin dose will be studied by regression analysis to evaluate the relative contribution of each of these parameters to the improvement in post-prandial blood sugars

*10.2 Provide a power analysis.*

*Response:* A previous study (5) in adults with well-controlled diabetes demonstrated that liraglutide treatment decreased mean weekly blood sugars by 22 mg/dL. Based on these results, *a priori* power analysis indicates that 9 subjects will need to be enrolled in the study to detect a change in mean weekly blood sugars of  $22 \pm 20\text{ mg/dL}$  between untreated and treated periods with 80% power and alpha error of 0.05 (paired t-test). We will enroll up to 12 subjects for this study.

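### Section 11.7 judges harm only by severe hypoglycemia against an unnamed historical rate, and no between-week comparison of recorded hypoglycemia episodes is planned

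*Combined protocol and SAP*

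**What the plan says.** Section 11.7 asks for the statistical tests on the safety data. The answer has two parts: "Number of severe hypoglycemic events will be documented", and "The rate of severe hypoglycemia will be compared to historical data". It gives no historical source, reference rate, definition of a severe event, test or error level.

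Other sections bear on the same question:

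- **Safety endpoints (end of section 7).** The list includes "Rates of hypoglycemia", not limited to severe events.
- **Data collected (8.2).** From Visit 1, "Subjects will be asked to keep a record of any episodes of hypoglycemia". From Visit 2 a diary covers hypoglycemia and other side effects in the treated week. CGM is worn in both weeks.
- **Planned analysis (7.1, 10.1).** Time below 70 and below 40 mg/dL is a secondary endpoint, compared within subject by t-test, paired t-test or Wilcoxon test. Recorded episodes are not mentioned.
- **Exploratory Aim 1 (1.3).** The type, number and rate of adverse events will be determined, with no comparison between weeks.
- **Insulin (8.2, Visit 2).** At the visit where liraglutide starts, "Basal rates will be decreased by 25% and meal boluses will be decreased by 33" per cent.
- **Withdrawal (12.1, 12.2).** Severe hypoglycemia is a ground for withdrawal. A withdrawn subject's data are left out of the analysis and the subject is replaced.

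**The concern.** The one comparison offered as a test of harm uses a rare event, a very short exposure and a reference that is not named. A result of no severe events could be read as reassurance when it excludes very little. If one event occurs, whether it counts as a signal depends on a rate that could be picked after the data are seen.

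Each subject also contributes an untreated week in which hypoglycemia episodes are recorded. These are more frequent than severe events by definition, and they concern a named safety endpoint. The plan collects them in both weeks and then specifies no contrast between the weeks.

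At stake is what this pilot can say about hypoglycemia to the designers of the longer placebo-controlled studies that section 14.1 has in view.

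**Working it through.** **1. The plan's own sample size.** Section 10.2 states that "power analysis indicates that 9 subjects will need to be enrolled in the study", for a change of 22 ± 20 mg/dL "between untreated and treated periods with 80% power and alpha error of 0.05 (paired t-test"). Reading 20 as the SD of paired differences and the test as two-sided, d = 22/20 = 1.1. Noncentral-t power is 76.1% for n = 8, 82.3% for n = 9 and 93.3% for n = 12. The figure of 9 is reproduced. It was set for mean glucose; no figure is given for safety.

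**2. Treated exposure.** Section 10.2 also says "We will enroll up to 12 subjects for this study", and treatment lasts 7 days.

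- 12 subjects: 12 × 7 / 365.25 = 0.230 person-years.
- 9 subjects: 9 × 7 / 365.25 = 0.172 person-years.

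**3. What zero severe events would exclude.** For a Poisson count of zero, the upper limit of a two-sided 95% interval is −ln(0.025) / exposure.

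- 12 subjects: 3.689 / 0.230 = 16.0 per person-year.
- 9 subjects: 3.689 / 0.172 = 21.4 per person-year.

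**4. How far the result depends on the reference rate.** The documents give no rate, so I assume 0.05 to 1.0 per person-year, treated as fixed and known. The one-sided p-value for one event in 12 subjects is 1 − exp(−rate × 0.230). The last two columns give power of the one-sided 0.05 exact Poisson test.

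| Assumed rate | Expected events | p for one event | Events needed | Power, 3-fold rise | Power, 10-fold rise |
|---|---|---|---|---|---|
| 0.05 | 0.01 | 0.011 | 1 | 3% | 11% |
| 0.1 | 0.02 | 0.023 | 1 | 7% | 21% |
| 0.2 | 0.05 | 0.045 | 1 | 13% | 37% |
| 0.3 | 0.07 | 0.067 | 2 | 2% | 15% |
| 0.5 | 0.12 | 0.109 | 2 | 5% | 32% |
| 1.0 | 0.23 | 0.205 | 2 | 15% | 67% |

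One event is significant against 0.2 and not against 0.3. Power for a tripling never exceeds 15%.

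**5. Would a paired test of severe events alone do better?** No. By the exact McNemar (sign) test, five subjects with events only in the treated week give two-sided p = 2 × 0.5⁵ = 0.0625, and six give 2 × 0.5⁶ = 0.031. So a 6–0 split is needed. For a 10-fold rise over the same assumed rates, one-sided power of the exact paired-rate test is 0% to 6.8%, against 11% to 67% for the historical comparison.

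**6. What a paired analysis of a more frequent measure could show.** A two-sided 0.05 paired t-test has 80% power for a standardized difference of 0.89 with 12 subjects and 1.07 with 9. The documents give no SD for episode counts or time below threshold, so this cannot be turned into episodes or hours, and skewed data would lower the power.

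**The case against.** The strongest case against has four parts.

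- **The matched comparison already exists.** CGM time below 70 and below 40 mg/dL is compared within subject under 7.1 and 10.1. This stands for CGM time, so it would be wrong to infer that the untreated week is ignored for hypoglycemia. It does not cover recorded episodes, and 11.7 does not refer to it.
- **The comparator is not the cause of the low power.** This stands. A reader might infer that 11.7 cannot detect harm because it uses historical data. The 16 per person-year limit follows from exposure alone, and step 5 shows that pairing severe events would be weaker. Cannot is also too strong: one event would be significant against a fixed rate of up to 0.2, and at a true rate of 16 per person-year about 3.7 events would be expected (16.04 × 0.230), with a 2.5% chance of none.
- **The untreated week is confounded too.** This stands. The insulin reduction begins with the first dose, so the between-week contrast reflects both changes. It is a reason to label the contrast, not to omit it.
- **The nature of the historical data is unknown.** A reader might infer that it comes from patients without this protocol's insulin reduction or monitoring. The documents do not say so. Visit 1 collects each subject's own history of severe events, which could be what is meant. That ambiguity supports asking for the source to be named.

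This is also an unblinded pilot in which no powered safety test would be expected. That argues for a descriptive statement with intervals.

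**Conclusion.** The point holds in a limited form. Section 11.7 rests its answer on a comparison whose reference is unnamed and whose precision is very low: 0.23 person-years at most, with zero events compatible with about 16 per person-year (21 for 9 subjects). Recorded episodes, available from both weeks and belonging to a stated safety endpoint, have no planned between-week analysis. The change is worth making because it adds information at almost no cost, but it will not give the trial power for severe events.

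The exposure and zero-event limits assume Poisson events, full 7-day treated exposure and a count restricted to the treated week, which 11.7 does not state. The p-values and power figures also rest on the assumed historical rates.

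A related conflict needs settling. Section 11.7 says severe events will be documented, while 12.1 and 12.2 allow a subject withdrawn for severe hypoglycemia to drop out of the analysis and be replaced. Section 12.3 adds that data are expunged if withdrawal precedes de-identification. A reader might infer that such events will certainly be lost. The text does not go that far, since withdrawal is discretionary and 12.3 lets data already collected be used after de-identification. But nothing says that they stay in the safety count.

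**What to change.** Rewrite the answer to 11.7 as follows.

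- **(a)** Add a within-subject comparison of recorded hypoglycemia episodes, treated against untreated week, with a 95% CI. Cite the paired analysis of CGM time below 70 and below 40 mg/dL in 7.1 and 10.1 as the supporting safety analysis.
- **(b)** State what counts as severe, list severe events individually with an exact CI for the rate, and make no claim of a powered test. Name the source and value of any historical rate beforehand and use it only as descriptive context.
- **(c)** State that the between-week contrast reflects liraglutide together with the simultaneous insulin reduction. The size of that reduction must also be reconciled: meal boluses are cut by 33% in 8.2 and by 30% in 13.1.
- **(d)** Reconcile 11.7 with 12.2, and with the expunging rule in 12.3, so that events in subjects withdrawn for severe hypoglycemia stay in the safety count.

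No new data collection is needed. The cost is revised wording, one extra paired analysis, and a safety statement that is openly imprecise.

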## **12.0 Withdrawal of Subjects**

*12.1 Describe anticipated circumstances under which subjects will be withdrawn from the research without their consent.*

Response: A subject may be withdrawn from the study if they are having significant side effects to liraglutide – nausea/vomiting, severe hypoglycemia. In addition, a subject may be withdrawn if they are having difficulty completing the study tasks essential for data collection.

*12.2 Describe any procedures for orderly termination.*

Response: Subject data will not be included in the analysis, and the subject will be replaced. All subjects will receive study compensation even if they are not included in the final study analysis.

*12.3 Describe procedures that will be followed when subjects withdraw from the research, including partial withdrawal from procedures with continued data collection.*

Response: If a subject is withdrawn from the research prior to de-identification of data, no data will be used for the subject. The data will be expunged and the subject will be replaced. If a subject withdraws from the study after de-identification of data, no further data will be collected for that subject. However, any data already collected may be included in the final analysis.

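### Sections 12.2 and 12.3 drop withdrawn subjects' data with no exemption for safety events, so severe hypoglycemia and other adverse events can leave the rates meant to count them

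*Combined protocol and SAP*

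**What the plan says.** **Withdrawal.** Section 12.1 is discretionary: "A subject may be withdrawn from the study if they are having significant side effects to liraglutide". It gives nausea/vomiting and severe hypoglycemia as examples, and adds difficulty completing study tasks as a further ground.

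**Data after withdrawal.** Section 12.2: "Subject data will not be included in the analysis, and the subject will be replaced". Section 12.3 says that if a subject is withdrawn before de-identification, none of the subject's data are used: "The data will be expunged and the subject will be replaced". For withdrawal after de-identification, "any data already collected may be included in the final analysis". The date of de-identification is not given.

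**Safety measures that depend on these data.**
- Section 11.7 documents the number of severe hypoglycemic events and continues: "The rate of severe hypoglycemia will be compared to historical data". It does not name the historical source or say when the comparison is made.
- The safety endpoints in section 7.1 include hypoglycemia rates, nausea/vomiting, anorexia, injection site reactions and pancreatitis.
- Exploratory Aim 1 (section 1.3) determines the type, number and rate of adverse events.

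**Study-level review.** On how often cumulative data are reviewed, section 11.6 answers "Response: see above". The answers above it give no interval. Section 11.1 adds: "All unforeseen events during the study tasks will be reported immediately to the principal investigator; if necessary, they will be reported to the IRB". Section 11.8 asks what suspends the research and answers "Response: Episode of pancreatitis".

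**The concern.** A rule that removes withdrawn subjects and replaces them is already awkward for efficacy. For safety it is worse, because withdrawal can be caused by the outcome being measured. A subject with severe hypoglycemia may be withdrawn for it, and the event then leaves both the count and the denominator. A replacement without an event may take the subject's place. The same applies to nausea and vomiting under Exploratory Aim 1.

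With at most 12 subjects, one or two lost events decide what the report says. Section 14.1 states that the results may be used to develop longer randomized trials, so a falsely clean safety record in subjects aged 15 to 21 could carry forward. Section 13.1 itself foresees hypoglycemia with the drug, so this is not a remote outcome.

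**Working it through.** **Inputs.** The plan gives a maximum of 12 subjects (sections 10.2 and 22.1) and 7 days of treatment each. It gives no rate of severe hypoglycemia and no withdrawal rate, so every rate below is an assumption. The plan's only computable figure is the efficacy sample size of 9. It reproduces: a two-sided paired t-test with a difference of 22 and SD of 20 mg/dL has 76.1% power at n = 8 and 82.3% at n = 9. The present point does not depend on it.

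**Step 1: direction of the bias.** Let p be the true chance that a treated subject has severe hypoglycemia. Let w be the share of affected subjects who are withdrawn and removed, and v the share of event-free subjects who are removed (for nausea or task difficulty, for example). The analysed proportion is

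p(1 − w) / [p(1 − w) + (1 − p)(1 − v)].

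This is below p exactly when w > v, equal to p when w = v, and above p when w < v.

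**Step 2: size when only affected subjects are removed (v = 0).** The formula becomes p(1 − w)/(1 − pw).

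| Assumed p | w = 0.25 | w = 0.5 | w = 1 |
|---|---|---|---|
| 5% | 3.8% | 2.6% | 0% |
| 10% | 7.7% | 5.3% | 0% |
| 20% | 15.8% | 11.1% | 0% |

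At p = 10%, the chance that 12 retained subjects show no event is 28% with w = 0, 52% with w = 0.5 and 100% with w = 1.

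**Step 3: size when event-free subjects are also removed.** Take p = 10% and v = 0.2.
- w = 0.5: 0.05/(0.05 + 0.72) = 6.5%, still below 10% but less so than the 5.3% at v = 0.
- w = 0: 0.10/(0.10 + 0.72) = 12.2%, so the rate is overstated.

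The overstatement in counts: 15 dosed, one affected subject who stays in, three withdrawn for nausea. The true 1/15 (6.7%) is analysed as 1/12 (8.3%).

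**Step 4: counts at this trial's scale.** Suppose two affected subjects are both withdrawn. The plan does not say whether replacements count toward the 12.
- If they do: 12 dosed, true 2/12 (16.7%), analysed 0/10.
- If they do not: 14 dosed, true 2/14 (14.3%), analysed 0/12.

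**Step 5: would a suspension trigger make up for this?** Assume 12 subjects dosed one at a time and a pause at the second subject with severe hypoglycemia. The trigger is met when at least two of 12 are affected: 0.6%, 2.3% or 12% of studies at p = 1%, 2% or 5%. The expected number of subjects still undosed at that point, averaged over all studies, is 0.02, 0.08 or 0.44, and overlapping dosing lowers it further. Such a trigger protects few subjects at low rates. It does not replace keeping the events in the analysis.

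**The case against.** **The direction is not fixed.** Section 12.1 also allows withdrawal for nausea/vomiting and task difficulty, and section 13.1 lists nausea among the most common side effects. Removing those subjects shrinks the denominator and pushes the severe hypoglycemia rate up. This stands: a reader might infer that the rules always bias the rate downward, and steps 1 and 3 show that they do so only when w > v.

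**Events may survive.** Withdrawal is discretionary, section 11.7 has severe events documented, section 13.1 makes the investigators responsible for recording adverse events, and section 12.3 permits collected data to be kept after de-identification. The analysis meant in section 12.2 could also be the efficacy analysis alone. This stands in part: a reader should not infer that events go unrecorded or are certain to be lost. But recording does not return an event to the analysed rate. Section 12.3 is permissive and tied to an undated step, and neither section limits itself to efficacy.

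**Withdrawals may not happen.** Section 22.2 expects every enrolled subject to complete. If so, the problem does not arise, but a withdrawal rule matters only when that expectation fails.

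**Subject-level care exists.** Insulin is reduced in advance. Subjects call in for persistent lows, highs or ketones, and insulin is raised for hyperglycemia or ketones. Visit 3 collects the hypoglycemia diary and reviews blood sugars and pump settings. A reader might infer from section 11.8 that severe hypoglycemia is unmanaged; the documents do not support that. Which events suspend a small single-centre pilot is a design choice, and the gaps in sections 11.6 and 11.7 are mainly missing detail.

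**Conclusion.** The point holds for the data-handling rules. Sections 12.2 and 12.3, followed as written, can remove events from the safety measures because those events occurred, and nothing in the plan exempts safety data.

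Downward bias in the severe hypoglycemia rate rests on one assumption: that affected subjects are withdrawn more often than event-free ones. That is likely, since the event is itself a withdrawal ground, but it is not certain. The size cannot be determined from the documents. It ranges from none, if no affected subject is removed and no event-free subject is either, to complete loss of the signal if every affected subject is removed.

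The documents do not support treating the short list in section 11.8 as an error in itself. Additional triggers are a matter for the investigator and the IRB.

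**What to change.** **Change to make (sections 12.2 and 12.3).** State that the safety events and exposure of every subject who received at least one dose of liraglutide, including withdrawn and replaced subjects, stay in the numerator and denominator of all safety analyses: section 11.7, the section 7.1 safety endpoints and Exploratory Aim 1. Limit exclusion and replacement to the efficacy analysis. State also whether replacements count toward the 12.

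**Cost.** A few sentences, with no new tests, staff or subjects. If the expunging rule reflects a promise in the consent form, that wording would have to change too. The consent pages were not available for this review, so this could not be checked.

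**Suggestions only.**
- Section 11.6: review cumulative counts of severe hypoglycemia and ketosis before each new subject's Visit 2.
- Section 11.7: name the historical source and say when the comparison is made.
- Section 11.8: let the investigator and the IRB consider a pause-and-review trigger for severe hypoglycemia or ketoacidosis, knowing from step 5 that a two-subject hypoglycemia trigger would rarely be met at low rates. The cost is a possible short enrolment pause within the 4-year window.
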